11.2 Exclusion criteria

- Primary Central Nervous System Lymphoma
- Patients with CNS Involvement of Lymphoma
- History of autoimmune disease, including but not limited to:
 - Inflammatory Bowel Diseases (Crohn's Disease, Ulcerative Colitis, Celiac Disease)
 - Systemic Lupus Erythematosus
 - Grave's Disease
 - Myasthenia Gravis
 - Rheumatoid Arthritis
 - Wegner's Syndrome
- Patients with history of drug reaction and eosinophilia systemic syndrome (DRESS) or toxic epidermal necrolysis (TEN)
- History of Human Immunodeficiency Virus (HIV), active Hepatitis C Infection or active Hepatitis B infection as defined by:
 - Patients with a positive hepatitis B surface antigen [HBsAg] or hepatitis C antibody [HCV Ab] will be excluded

Protocol Title: Duvelisib Exposure to Enhance Immune Profiles of T Cells in Patients with Diffuse Large B Cell Lymphoma (DEEP T CELLS)

- Patients with a positive hepatitis B core antibody (HBcAb) must have negative hepatitis B virus (HBV) deoxyribonucleic acid (DNA) to be eligible and must be periodically monitored for HBV reactivation by institutional guidelines
- Patients with known active cytomegalovirus (CMV) or Epstein-Barr virus (EBV) infection (i.e., subjects with detectable viral load)
- Patients with ongoing treatment for systemic bacterial, fungal or viral infection
- Patients with history of immune or drug mediated colitis, hepatitis or pneumonitis
- Patients with history or concurrent condition of interstitial lung disease of any severity and/or severely impaired lung function
- Patients with previous treatment with a PI3K inhibitor
- Patients currently on immunosuppressive therapy, including steroids
- Previous CD 19 directed therapy
- Patients who have had chemotherapy or radiotherapy within 2 weeks (6 weeks for nitrosoureas or mitomycin C) prior to entering the study or those who have not recovered from adverse events due to agents administered more than 2 weeks earlier (i.e., have residual toxicities > Grade 1).
- Patients receiving any other investigational drugs.
- Pregnant women are excluded from this study because duvelisib is agent with the potential for teratogenic or abortifacient effects. Because there is an unknown but potential risk for adverse events in nursing infants secondary to treatment of the mother with duvelisib, breastfeeding should be discontinued if the mother is treated with duvelisib and breastfeeding should not be resumed until at least 1 month after last dose of duvelisib.
- Patients with history of chronic liver disease or veno-occlusive disease
- Patients that are unable to receive prophylactic treatment for pneumocystis, herpes simplex virus (HSV), or herpes zoster (“VZV) at screening
- Patients with history of tuberculosis treatment within the 2 years prior to randomization
- Patients with prior surgery or gastrointestinal dysfunction that may affect drug absorption (e.g., gastric bypass surgery, gastrectomy). Subjects with clinically significant medical condition of malabsorption, inflammatory bowel disease, chronic conditions which manifest with diarrhea, refractory nausea, vomiting or any other condition that will interfere significantly with drug absorption.
- Concurrent administration of medications or foods that are strong inhibitors or inducers of cytochrome P450 3A (CYP3A). No prior use within 2 weeks before the start of study intervention
- Administration of a live or live attenuated vaccine within 6 weeks of randomization

12. Local Number of Participants

We will be recruiting 20 patients at Winship. We are expecting to have to enroll (consent) 30 patients to reach our recruitment goal of 20.. Patients will be registered after signing of the informed consent document and meeting all entry requirements.

13. Recruitment Methods

Investigators, nurses (CRNs), research coordinators (CRCs) and/or data managers review lists of patients who have DLBCL or relapsed/refractory follicular lymphoma and will determine if there are patients who might be eligible for the clinical trial. The CRN/CRC/data manager reviews accessible medical records to screen further for eligibility. The CRN/CRC reviews the eligibility with the physician.

Patients will be identified by their treating physicians. Clinical care team at Winship will inform potential patients about the known benefits and potential risks of a clinical trial as well as other available treatment options.

Protocol Title: Duvelisib Exposure to Enhance Immune Profiles of T Cells in Patients with Diffuse Large B Cell Lymphoma (DEEP T CELLS)

Some of the patients recruited for this protocol will be patients being treated at Emory and under the care of one or more of the study investigators. Some potential patients will be identified by their community treating physician and referred to Emory for possible participation in the clinical trial.

No incentives are provided to patients for trial participation.

Study personnel will notify Winship Central Subject Registration (WCSR) by email at [contact], once a patient has been consented for a trial.

Email notification must be done within 24 hours after consent has been obtained and it will include scanned copies of:

- Signed patient consent form
- HIPAA authorization form
- Emory Research Management System (ERMS; <https://erms.emory.edu>) Enrollment Fax

Cover

The WCSR will enter the subject into the OnCore Research Management System, which is the system of record for Winship Cancer Institute Clinical Trials.

14. Withdrawal of Patients

All study patients have the right to withdraw from the study at any time. The reasons for withdrawal must be documented in the case report form. Final study evaluations will be done at the time of withdrawal. The following are examples of early withdrawal from the study:

- Patient withdrawal of consent at any time
- Any medical condition that the primary investigator or sponsor believes may jeopardize the patient's health or safety if they continue in the study
- Non-compliance (frequent missed visit, doses)
- Pregnancy
- Rapid progression of disease (ie: increasing/symptomatic lymphadenopathy) that would require alternative treatment prior to CAR T cell leukapheresis
- Termination of the study by the primary investigator, sponsor or FDA

15. Risks to Participants

- **Additional blood draws** - The physical risk of drawing blood is local pain and bruising at the site of venipuncture. Qualified phlebotomists or designee will draw blood samples. Care will be taken to obtain these specimens in a safe and hygienic manner. A small number of people experience lightheadedness or fainting. There is a slight risk of infection. To minimize these risks, attempts will be made to draw study blood samples at the same time as blood draws needed for routine clinical care are obtained. Repeated blood drawing may be associated with iron deficiency anemia.
- **Data security** - Subjects will be asked to provide personal health information (PHI). All attempts will be made to keep this PHI confidential within the limits of the law. However, there is a chance that unauthorized persons will see the subjects' PHI. All records will be kept in a locked file cabinet or maintained in a locked room at the participating sites. Electronic files will be password protected behind an academic institutional firewall. Only people who are involved in the conduct, oversight, monitoring, or auditing of this study will be allowed access to the PHI that is collected. Any

Protocol Title: Duvelisib Exposure to Enhance Immune Profiles of T Cells in Patients with Diffuse Large B Cell Lymphoma (DEEP T CELLS)

publications from this study will not use information that will identify subjects. Organizations that may inspect and/or copy research records maintained at the participating sites for quality assurance and data analysis include groups such as the National Cancer Institute (NCI) and Food and Drug Administration (FDA).

16. Potential Benefits to Participants

There is no guarantee of benefit to subjects who enroll in this protocol.

17. Data Management and Confidentiality

17.1 Source Documents:

Source data is all information, original records of clinical findings, observations, or other activities in a clinical trial necessary for the reconstruction and evaluation of the trial. Examples include medical records (hospital records, office charts), laboratory results, imaging scans and reports, EKG's, patient diaries, videos, photographs, pharmacy dispensing, and other records, investigator or patient completed questionnaires involved in the clinical trial.

17.2 Case Report Forms:

The case report form (CRF) will be the primary data collection instrument for the study. All data requested on the CRF will be recorded and all entries will be recorded into an electronic data capture system by authorized personnel. The principal investigator is responsible for assuring that the data entered into the CRF are complete, accurate and that entries are updated in a timely fashion. Data will be entered in the clinical management system - Online Collaborative Research Environment (ONCORE)- per Winship SOP 4.2 Data Completion Metrics. OnCore will be used to record all study related information for all registered subjects, including their assigned patient ID and assigned dose cohort. All data submitted must be accompanied by supporting source documents, where applicable and as outlined in the protocol-specific monitoring plan. Data completion will be reviewed monthly. In situations where there are significant delays of data completion, the Associate Director of Clinical Research or the Director of Clinical Trials may temporarily suspend enrollment.

All data must be entered in the timeframe required at each site, but no later than 30 days following registration and each visit completion. All queries are to be resolved within 4 weeks of issue. The coordinating center multi-site coordinator will provide OnCore training and request access to the appropriate staff at the participating site.

17.3 Data Retention:

All study documents will be retained for at least two years after the last approval of a marketing application in their country and until there are no pending or contemplated marketing applications in their country.

17.4. Transmission of Data:

. Emory University will cover the cost of shipment of blood samples. All patient samples for T-cell phenotyping will be analyzed at Emory University to ensure uniform analysis. Clinical data (ORR and rates of CRS, neurotoxicity, ICU transfers) will be captured with chart review at both Emory University. Data will be uploaded onto OnCore.

17.5 Statistical Plan:

17.5.1 Study Design Endpoints

This is pilot study to examine if exposure to a dual PI3K delta and gamma inhibitor before CAR T cell leukapheresis leads to decreases in manufacturing time and enhanced expression of CD27/CD28+ T cells. Patients who receive at least 75% (23/28 doses) of duvelisib will be evaluable for final analysis. Patients who do not receive 75% of doses will be considered unevaluable and replaced. Patients who do not undergo leukapheresis within two (2) days of completion of the 8 to 15 days of duvelisib will be considered unevaluable and replaced. All patients with any exposure to duvelisib will be evaluable for toxicity (please see section 13.3 on grading of toxicities).

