4.2.2. Formulation, Appearance, Packaging and Labeling

Duvelisib comes in two strengths: 15mg and 25mg. Patients will be provided twenty-eight (28) 25mg tablets. The contents of the label will be in accordance with regulatory requirements.

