5.1 Study Design

This is an open-label pilot clinical trial prospective study of treating patients with relapsed/refractory DLBCL or relapsed/refractory follicular lymphoma with duvelisib at a dose of 25 mg p.o. b.i.d. for 8 to 15 days prior to collection of mononuclear cells by apheresis for the purpose of CAR-T manufacturing. The intended duration of duvelisib exposure is 2 weeks. The duration of duvelisib may be adjusted to a period between 8 and 15 days depending upon the schedule of apheresis, with the last dose of duvelisib on the day of apheresis.

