5.3 Interruption/Disruption of Treatment

Duvelisib is a BID medication. Doses that are missed or not absorbed (i.e., vomiting) will not be made up with additional dosing after the 8 to 15 day study period.

Duvelisib can be stopped for any clinically significant toxicity, including if any of the following are observed:

- Grade 3 or 4 hematologic toxicity (19) as defined by the CTCAE version 5.0)
- Grade 3 or 4 non-hematological toxicity

For grades 1-2 as defined by the CTCAE, will not have any dose modifications and will be treated with supportive care. If study drug is stopped due to an AE, it will not be resumed, and the patient may proceed to leukapheresis on schedule. No allowance will be made for dose interruptions

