17.5.2 Analysis of Primary Endpoints

All patients that complete >75% of planned duvelisib doses and undergo leukapheresis within 2 weeks of duvelisib treatment completion will be included in the final analysis of the primary endpoint. The primary endpoint of the study to estimate the fold-change increase in CD27/CD28 double positive T cells following *in vivo* exposure to duvelisib from baseline to day 15. Our in vitro studies have shown that culturing DLBCL patients' T cells with 14 days of duvelisib increased the amount of CD27/CD28 double positive T cells from 12.2% to 32.7% (Petersen, et al, supplemental data). However, there are currently no *in vivo* background data to benchmark the expected fold-change CD27/CD28 double positive T cells over a 14-day window. Therefore, with 20 patients, this pilot study will be based on estimation on the fold change increase only and will not include a formal evaluation of the change against a null unpromising fold-change. However, we will consider this study promising if there is at least a two-fold increase in CD27+/CD28+ in at least 75% of patients.

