17.5.3 Analysis of Secondary Endpoints

- 1). Descriptive statistics will be used to calculate the proportion of patients that completed at least 75% of duvelisib doses as documented by the patient pill diaries. The proportion along with an exact 95% confidence interval will be reported.
- 2). Descriptive statistics will be used to calculate the median manufacturing time from the 10 patients that completed at least 75% of duvelisib doses. The median will be reported along with the minimum and maximum manufacturing times.
- 3). A Wilcoxon signed-rank test will evaluate the change in proportion of CD27+/CD28+ and CD4-/CD8- T cells at baseline and at day 15
- 4). Descriptive statistics will be used to calculate the *in vivo* expansion and persistence of CAR-T 19 cells post infusion as measured by serial CAR-T 19 PCR measurements.
- 5). The ORR (complete response or partial response) will be summarized along with an exact 95% confidence interval. Disease response will be based on the RECIST criteria (version 1.1). Please see section 8.2 on the definitions of disease response.

6). The 90 day PFS and OS will be estimated using the Kaplan-Meier method and calculated with corresponding 95% confidence intervals. Please see section 8.3 on the definitions of progressive disease.

7). Descriptive statistics will be used to calculate the frequency of ICU transfers due to CRS and/or neurotoxicity. Descriptive statistics will also be used to calculate the frequency of administration of tocilizumab and/or corticosteroids use for CRS and/or neurotoxicity.

8). Descriptive statistics will be used to assess the frequency of all grade toxicities as defined by CTCAE (version 5.0).

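### Section 17.5.1 equates 75% of doses with 23 of 28; 75% of 28 is 21, the count conflicts with 17.5.2, and taken literally it cannot be met on 8- to 11-day courses

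*Combined protocol and SAP*

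**What the plan says.** Section 17.5.1 of the combined protocol and SAP gives the threshold as both a percentage and a count: "Patients who receive at least 75% (23/28 doses) of duvelisib will be evaluable for final analysis". The consequence of missing it follows: "Patients who do not receive 75% of doses will be considered unevaluable and replaced".

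Section 17.5.2 describes the primary analysis set differently: "All patients that complete >75% of planned duvelisib doses". It uses a strict inequality, refers to planned doses and gives no count. Section 17.5.3 item 1 reports "the proportion of patients that completed at least 75% of duvelisib doses as documented by the patient pill diaries", and item 2 uses the same percentage to select patients for manufacturing time. Neither item states a count or a denominator. Section 5.7 repeats 23/28 next to 75% as an example of severe noncompliance.

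On course length, section 5.1 says "The intended duration of duvelisib exposure is 2 weeks" and then "The duration of duvelisib may be adjusted to a period between 8 and 15 days depending upon the schedule of apheresis". Dosing is twice daily. Section 4.2.2 says "Patients will be provided twenty-eight (28) 25mg tablets", which matches 14 days.

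**The concern.** The percentage and the count in 17.5.1 are not the same number, so the rule contradicts itself. The count also presumes 28 planned doses, although the design lets the course run from 8 to 15 days.

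These sentences decide who enters the primary analysis and who is replaced, and hence which 20 patients make up the result. Two analysts with the same dosing data could build different primary sets. On shorter courses, the count would make inclusion depend on when apheresis was scheduled rather than on adherence.

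Section 17.5.2 calls the study promising if at least 75% of patients show a two-fold increase, which is 15 of 20. If the result sits at that boundary, exchanging one responder for a replacement who does not respond gives 14/20 = 70% and reverses the reading.

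**Working it through.** **Inputs.** Threshold 75% and count 23/28 (17.5.1); more than 75% of planned doses (17.5.2); two doses a day for 8 to 15 days, intended 2 weeks (5.1).

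**The plan's own figure.** 0.75 × 28 = 21, while 23/28 = 0.821. The stated equivalence does not reproduce. For comparison, 21/28 = 75.0% and 22/28 = 78.6%. The count would fit 30 doses: 0.75 × 30 = 22.5, rounded up to 23. The documents do not say that this is its origin.

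**Minimum doses by course length.** With d days and both doses taken every day, planned doses are n = 2d. The minimum is ceil(0.75n) for at least 75%, and floor(0.75n) + 1 for more than 75%.

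| Days | Planned doses | Count of 23 | At least 75% | More than 75% | 23 as share of planned |
|---|---|---|---|---|---|
| 8 | 16 | unreachable | 12 | 13 | – |
| 9 | 18 | unreachable | 14 | 14 | – |
| 10 | 20 | unreachable | 15 | 16 | – |
| 11 | 22 | unreachable | 17 | 17 | – |
| 12 | 24 | 23 | 18 | 19 | 95.8% |
| 13 | 26 | 23 | 20 | 20 | 88.5% |
| 14 | 28 | 23 | 21 | 22 | 82.1% |
| 15 | 30 | 23 | 23 | 23 | 76.7% |

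The three rules agree only at 15 days with 30 doses. That row assumes 30 doses are available, whereas 4.2.2 provides 28 tablets.

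The two percentage rules differ only where exactly 75% is attainable: 12/16, 15/20, 18/24 and 21/28.

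**Sensitivity to the last day.** Section 5.1 puts the last dose on the day of apheresis but does not say how many doses are taken that day. With one, n = 2d − 1, which runs from 15 to 29.

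- The maximum at 8 to 11 days is 15, 17, 19 and 21 doses, so 23 is still unreachable.
- At 12, 13, 14 and 15 days, 23 doses is 100%, 92.0%, 85.2% and 79.3% of planned.
- No exact 75% tie arises, so the two percentage rules coincide.

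**Why the denominator must be fixed in advance.** Section 5.3 says: "If study drug is stopped due to an AE, it will not be resumed, and the patient may proceed to leukapheresis on schedule". Take a patient with a 28-dose plan who stops after 18 doses. Against the plan that is 18/28 = 64.3%, not evaluable. If the course is afterwards described as a 9-day course, it is 18/18 = 100%, evaluable. No section says when the planned number is set.

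**The case against.** The best defence is that the operative words are the percentage and the count is only a parenthetical illustration for the intended 14-day course, wrongly calculated. The sentence that triggers replacement carries no count, the same paragraph of 17.5.1 acknowledges courses of 8 to 15 days, and 17.5.2 speaks of planned doses. On that reading short courses can be evaluable. What remains is at most one dose between the two inequalities, plus a dispute about patients with exactly 21 or 22 of 28 doses, in a pilot that only estimates and does not test.

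Much of this is fair. The short-course exclusion does depend on applying the count literally, and it is stated here on that condition. But the defence itself concedes that the count is wrong. It also leaves two inequalities in force and the planned number undefined, and the conflict exists at the intended 14 days without any appeal to short courses. With 20 patients, membership of the set matters even without a formal test.

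Two further objections deserve an answer. Nothing in the protocol authorises relabelling a course after an adverse event, and dose changes must already be documented. That is true, so the example shows a gap rather than a permitted practice. It is also said that the documents do not show whether the percentage or the count is the slip. However, the percentage appears in every statement of the rule (5.7, 17.5.1, 17.5.2 and 17.5.3), while the count appears only in 5.7 and 17.5.1, each time as a gloss on 75%. Dropping the count therefore has support in the text.

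**Conclusion.** The rule is wrong as written and must be fixed before analysis. The count overstates the 75% threshold by two doses of 28 (82.1% against 75%). Sections 17.5.1 and 17.5.2 give different primary sets, with cutoffs of 21, 22 or 23 at the intended duration if 28 doses are planned. Applied literally, the count cannot be met on 8- to 11-day courses, whether the apheresis day has one dose or two.

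The number of patients affected is unknown, because the documents give an intended duration but no distribution of course lengths. Toxicity evaluability is unaffected: 17.5.1 counts every patient with any exposure.

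**What to change.** - Delete the 23/28 count from 17.5.1. Define evaluability for analysis as doses taken divided by doses planned for that patient's own course, at least 75%.
- Fix the planned number prospectively. Record it on the CRF, with the date, when apheresis is scheduled, and state how doses on the apheresis day are counted. Allow it to change only if apheresis is rescheduled, not because doses were missed or the drug was stopped early.
- Use the same denominator and inequality in 17.5.1, 17.5.2 and 17.5.3 items 1 and 2.
- Reconcile section 5.7, which reuses 23/28 as a ground for discontinuation, and section 4.2.2, where 28 tablets are provided for a course that may last 15 days. No clinical rule is proposed for either.

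The two sections also state different leukapheresis windows (2 days in 17.5.1, 2 weeks in 17.5.2). That is a separate point, but the primary sets will not match until it too is settled.

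The cost is wording changes in three sections, reconciliation of two others and one CRF field for planned doses with the date set. No extra patients are needed.

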Protocol Title: Duvelisib Exposure to Enhance Immune Profiles of T Cells in Patients with Diffuse Large B Cell Lymphoma (DEEP T CELLS)

Endpoints:	
Primary Endpoint:
 
• The fold increase in the proportion of T cell phenotypes expressing CD 27/28 (to overall T cell count) after 8 to 15 day exposure to duvelisib 
Secondary Endpoints:
 
• The proportion of duvelisib consumed as evaluated by the patient pill diaries.• Manufacturing time of CAR-T 19 cells in weeks (includes manufacturing failure)• The proportion of CD27/28 double positive T cells and CD4/8 double negative T cells• CAR-T kinetics assessment by PCR• Overall response at 90 days after CAR-T cell infusion defined by the Tumor Response Assessment that are complete responders (CR) and partial responders (PR).• Progression-free Survival (PFS) at 90 days per RECIST 1.1 and Overall Survival at 90 days• ICU transfer due to CRS and/or neurotoxicity or due to the treatment with tocilizumab and/or corticosteroids• Grade III-V toxicities (as defined by CTCAE version 5.0)
Study Population:	20 patients will be enrolled with relapsed/refractory DLBCL or relapsed/refractory follicular lymphoma
Phase:	Pilot
Description of Sites/Facilities Enrolling Participants:	This study will be at Winship Cancer Institute, Emory University.
Description of Study Intervention:	Duvelisib is an oral PI3K inhibitor that is given at a dose of 25mg BID prior to manufacturing of CAR-T cells.
Study Duration:	We estimate that the duration of the study will be approximately 18 months.

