5.7 Description of Study Procedures

Definition of Study Assessments

All patients will be closely monitored for safety and tolerability throughout the study. Patients will continue dosing until they experience intolerable AE's, patient withdrawal or termination of the study. Patients may be discontinued from study treatment in the following situations: 1) patients has decided to withdrawal from the study, 2) Intolerable adverse events, 3) confirmed disease progression or lack of benefit, 4) pregnancy, or 5) severe noncompliance (including but not limited to receiving less than 75% of duvelisib doses (23/28 doses). The schedule of activities is listed in section 1.3.

Medical History

Medical history and demographics will be collected at screening. Medical history will include other significant co-morbidities, previous surgeries, cancer history, previous chemotherapy and outcomes, use of tobacco, alcohol and recreational drugs and any known toxin exposure. Demographics data will include age, sex and self-identified race/ethnicity.

Performance Status

The ECOG performance status (see appendix A) will be assessed at screening and throughout the study (days 1, 8 and 15 during treatment with duvelisib; days 7,14,28,42 and 90 post CAR-T infusion).

Physical Exam

Physical exam will include examination of all body systems, including assessment of general appearance, weight, height, head, neck, lymph nodes, heart, lungs, abdomen, extremities, skin and nervous system. A physical exam will be performed on screening and on days 1,8 and 15.

Laboratory Data

Blood samples for chemistry, hematology, viral serologies, leukocyte immunophenotyping and pregnancy (for pre-menopausal patients) will be analyzed at Winship Cancer Institute laboratory. The chemistry panel will include sodium, potassium, chloride, bicarbonate, glucose, BUN, AST, ALT, total bilirubin, total protein, thyroid stimulating hormone and magnesium will be tested at screening and on days, 1,8 and 15. Hematology panel includes complete blood count, including white blood cell count with differential (neutrophils, lymphocytes, eosinophils, basophils), red blood cell count, hemoglobin, hematocrit and platelet count will be tested at screening and days 1, 8 and 15. Viral serologies will be tested at screening and include:

- HIV antigen/antibody
- Hepatitis B Panel (HBsAg, HBsAb, HBcAb and HBV DNA PCR if HBcAb is positive)
- Hepatitis C Panel (HCV Ab and HCV PCR if HCV Ab is positive)

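### The 23-of-28-dose evaluability rule in 17.5.1 excludes every 8- to 11-day course that 5.1 permits, and 17.5.2 applies a different dose rule and a day-15 time point

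*Combined protocol and SAP*

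**What the plan says.** **Dosing.** Section 5.1 sets 25 mg b.i.d. and says "The intended duration of duvelisib exposure is 2 weeks". It adds that "The duration of duvelisib may be adjusted to a period between 8 and 15 days depending upon the schedule of apheresis". Under the same section, dosing ends on the day the cells are collected. The Synopsis defines the primary endpoint as a fold increase in the CD27/CD28 proportion ("to overall T cell count) after 8 to 15 day exposure to duvelisib"), and the primary objective in Section 2 uses the same range. Section 4.2.2 supplies 28 tablets, and Section 5.3 does not allow missed doses to be made up.

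**Who is evaluable.** Section 17.5.1: "Patients who receive at least 75% (23/28 doses) of duvelisib will be evaluable for final analysis", and "Patients who do not receive 75% of doses will be considered unevaluable and replaced". It also requires leukapheresis within two days of finishing an 8- to 15-day course, as does Section 7.1. Section 17.5.2 defines the primary analysis set differently: "All patients that complete >75% of planned duvelisib doses", with leukapheresis within 2 weeks. *Planned* is not defined.

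**Other uses of the threshold.** Section 5.7 lists "receiving less than 75% of duvelisib doses (23/28 doses") as an example of severe noncompliance, one of several grounds on which a patient may be discontinued. Section 17.5.3 item 1 reports the proportion of patients completing at least 75% of doses and names no denominator.

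**Time point.** Sections 17.5.2 and 17.5.3 item 3 use baseline to day 15. Section 5.6 limits treatment-phase phenotyping to days 1 and 15, and Table 1 gives day 15 a window of ±2 days. Section 5.7 (Laboratory Data) instead places the second phenotyping before apheresis.

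**The concern.** The 23/28 count fits a fixed 14-day course, while the dosing section and the endpoint allow 8 to 15 days. Read literally, 17.5.1 makes a patient unevaluable who was dosed exactly as 5.1 permits and missed nothing, and has that patient replaced. The same paragraph treats 8 to 15 days as a completed course when it sets the leukapheresis clock.

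The primary analysis set is at stake. Section 17.5.2 calls the study promising if at least 75% of patients show a two-fold increase, and that proportion is taken over this set. If 17.5.1 and 17.5.2 select different patients, two analysts could report different denominators from the same data. Under any 28-dose reading, the result would describe courses of at least 11 or 12 days, not the 8 to 15 days in the endpoint. The toxicity analysis is not affected, because 17.5.1 keeps every exposed patient in it.

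**Working it through.** **Inputs.** Two doses a day, 8 to 15 days, last dose on the apheresis day (5.1); threshold 75%, written as 23/28 (17.5.1); more than 75% of planned (17.5.2); apheresis within two days of completion (7.1); day 15 ±2 (Table 1); 28 tablets (4.2.2). Assumption: two doses on every day, including the first and last.

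**Step 1: the plan's own figure.** 23/28 = 82.1%. 0.75 × 28 = 21. The stated count does not reproduce the stated percentage.

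**Step 2: what each permitted course can reach.** Maximum doses = 2 × days.

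| Days | Max doses | Reaches 23? | Reaches 21? | Max as % of 28 | At least 75% of own course | More than 75% of own course |
|---|---|---|---|---|---|---|
| 8 | 16 | no | no | 57.1 | 12 | 13 |
| 9 | 18 | no | no | 64.3 | 14 | 14 |
| 10 | 20 | no | no | 71.4 | 15 | 16 |
| 11 | 22 | no | yes | 78.6 | 17 | 17 |
| 12 | 24 | yes | yes | 85.7 | 18 | 19 |
| 13 | 26 | yes | yes | 92.9 | 20 | 20 |
| 14 | 28 | yes | yes | 100 | 21 | 22 |
| 15 | 30 (28 supplied) | yes | yes | 100 on 28 supplied | 23 of 30, or 21 of 28 | 23 of 30, or 22 of 28 |

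Four of the eight permitted lengths cannot reach 23 doses. Correcting only the count to 21 leaves three excluded.

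**Step 3: readings of 17.5.2.** If *planned* means the intended 2 weeks, more than 75% of 28 is at least 22 doses, and 8- to 10-day courses fail. If it means the patient's own course, an 8-day patient qualifies with 13 doses and no length is excluded. The minimum is therefore 23, 22, 21 or as few as 13, depending on the sentence and the reading.

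**Sensitivity.** With one dose on the last day, the 11- and 12-day maxima become 21 and 23. The 23-dose result is unchanged (8 to 11 days fail), but an 11-day course then also misses 22.

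**Step 4: adherence endpoint.** Against 28, a fully adherent 8-day patient scores 16/28 = 57%. Against the patient's own course, 16/16 = 100%. Item 1 does not say which applies.

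**Step 5: day 15.** The window covers days 13 to 17. With last dose on day L, apheresis falls on days L to L+2: L = 8 gives days 8–10, L = 9 gives 9–11, L = 10 gives 10–12. All precede day 13. For L = 11 the range is 11–13, which just touches it.

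**Step 6: replacements, illustration only.** Suppose a share f of treated patients has an 8- to 11-day course and there are no other losses. Reaching 20 evaluable patients under the 23-dose count needs 20/(1 − f) treated: f = 0 gives 20; 0.10 gives 22.2; 0.20 gives 25.0; 0.30 gives 28.6. That is 0 to about 9 extra patients. The documents give no value for f.

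**The case against.** **The rule may be a deliberate minimum exposure.** The intended duration is 2 weeks, shortening is allowed only for apheresis scheduling, and the in vitro rationale rests on 14 days. Limiting the primary set to near-2-week courses would be defensible. However, the objective and endpoint cover 8 to 15 days, no text restricts the set, and a minimum exposure would not be labelled 75% when the count is 82%.

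**The count may only illustrate a 14-day course.** The replacement sentence mentions 75% of doses without a count. This would ease the conflict, but nothing in the text says so.

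**Consequences are limited.** Section 17.5.2 is estimation only, and the two-fold benchmark is informal. That stands and limits the weight of the point.

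A reader might also infer three stronger things that the documents do not support:

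- *That 5.7 requires 23 doses.* It gives fewer than that as an example for which a patient may be discontinued; the binding rule is in 17.5.1.
- *That short-course patients would fail the adherence endpoint.* Item 1 never names 28. They could be scored that way.
- *That primary samples would be taken off drug and after collection.* Section 5.7 sets a pre-apheresis sample, 7.1 adds flow cytometry after apheresis, and the collection schema in Appendix D is a figure that could not be read here. What is shown is that the day-15 wording was not aligned with the pre-apheresis sample.

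**Conclusion.** The inconsistency is real and should be settled before analysis. Followed literally, 17.5.1 removes fully adherent patients at four of eight permitted course lengths, or three if the count is corrected to 21. Section 17.5.2 adds a second dose rule, a conflicting leukapheresis window and a time point that 8- to 10-day courses cannot meet before apheresis.

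The dose counts rest on two doses every day; the exclusion of 8- to 11-day courses at 23 doses also holds with a single dose on the last day. It would be tempting to conclude that the result is biased in a known direction. The documents do not support that: they give no in vivo time course and no distribution of course lengths, and the effect is nil if no course is short or if the response plateaus early.

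**What to change.** 1. **One dose rule** in 5.7, 17.5.1, 17.5.2 and 17.5.3 items 1 and 2: at least 75% of the b.i.d. doses scheduled from first dose to the final scheduled apheresis date. Delete 23/28. Update the denominator when apheresis is rescheduled within 8 to 15 days; if it stayed fixed, a patient booked for 14 days and moved to day 9 could take only 18 doses against a minimum of 21. Do not reduce it when a patient stops early for an adverse event or non-adherence. The minimums are 12/16, 14/18, 15/20, 17/22, 18/24, 20/26 and 21/28 for 8 to 14 days, and 23/30 for 15 days. Because 28 tablets are supplied, either supply 30 or state that a 15-day course is planned as 28 doses (minimum 21).
2. **One time point:** in 17.5.2 and 17.5.3 item 3, and in 5.6 and Table 1 to match, replace day 15 with the pre-apheresis sample of 5.7.
3. **One window:** in 17.5.2, change the leukapheresis limit from 2 weeks to two days.

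If the sponsor wants only near-2-week courses in the primary set, state that minimum in 17.5 and narrow the endpoint wording to match.

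The cost is a few sentences and one table entry. No new visit is needed, since 5.7 already calls for the pre-apheresis sample and 4.2.1 for the dose diary; supplying 30 tablets would add two per 15-day patient. The downside is a primary set with mixed exposure lengths. A descriptive display of fold change by days on drug would show this without altering the pooled benchmark.
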